7.4.8 Weeks 2, 3, and 4 (Doses 5, 6, 8, 9 and 11)

1. Symptom-directed physical examination
2. Vital signs
3. Oximetry
4. Concomitant medications review
5. AE review
6. Confirm administration of all routine pulmonary medications and airway clearance techniques prior to administration of study drug
7. Obtain blood for PK prior to dosing
8. Obtain pre-dose sputum for PK (prior to doses 5 and 6 only)
9. Administer study drug

7.4.9 Week 4 (Dose 12)

Pre-dose:

1. Complete physical examination (including body weight)
2. Vital signs
3. Oximetry
4. Concomitant medications review
5. AE review
6. Obtain blood and urine samples for PK prior to dosing
7. Administer any routine pulmonary medications and airway clearance techniques, including SABA and/or LABA, Pulmozyme, inhaled corticosteroids and/or antibiotics
8. Spirometry (FEV₁, FVC, and FEF₂₅₋₇₅)
9. Administer study drug

Post-dose:

1. Symptom-directed physical examination within 2 hours post dose
2. Vital signs within 2 hours post dose
3. Oximetry within 2 hours post dose
4. Spirometry at 20, and 60 minutes, 4 hours post dose
5. Obtain the following samples for PK:
 - Blood at 1, 2, 3, 4, and 8 hours post dose
6. Obtain sample for sweat chloride determination

7.4.10 Follow-up Visit for PK—24 hours +/- 12 hours After Last Dose

Subject to return to clinic to obtain serum and urine samples for PK. The samples can be collected any time within the time window specified.

7.4.11 Follow-up Visit for PK—96 hours +/- 48 hours After Last Dose

Subject to return to clinic to obtain serum and urine samples for PK. The samples can be collected any time within the time window specified.

7.4.12 Follow-up Visits—7 and 28 Days After Last Dose

Follow-up visits will occur 7 and 28 days after the last dose of study drug (dose 12).

If at any time during the study the subject discontinues the study early, the subject should return to the clinic to complete the End of Treatment Visit procedures below, and should also return to the clinic to complete the End of Study Visit procedures 28 days after the last study drug dose.

7.4.12.1 7 Days After Last Dose—End of Treatment Visit

1. Subject self-completes the CFQ-R prior to all other procedures and assessments
2. Complete physical examination (including body weight)
3. Vital signs
4. Oximetry
5. Concomitant medication review
6. AE review
7. Chest Xray
8. 12-lead ECG
9. Spirometry
10. Obtain blood and urine samples for local laboratory assessments
11. Obtain urine or blood for pregnancy test (for women of child-bearing potential)
12. Obtain blood samples for PK
13. Obtain sputum sample for the following local laboratory assessment:
 - Microbiology organism identification
14. Obtain blood and sputum samples for inflammatory biomarkers
15. Obtain sample for sweat chloride determination

7.4.12.2 28 Days After Last Dose—End of Study Visit

1. Subject self-completes the CFQ-R prior to all other procedures and assessments
2. Complete physical examination (including body weight)
3. Vital signs
4. Oximetry
5. Concomitant medication review
6. AE review
7. Spirometry
8. Obtain blood and urine samples for local laboratory assessments
9. Obtain urine or blood for pregnancy test (for women of child-bearing potential)
10. Obtain blood and sputum samples for inflammatory biomarkers

11. Obtain serum samples for PK
12. Obtain sample for sweat chloride determination

8.0 STUDY PROCEDURES

Safety parameters will be assessed by monitoring AEs, vital signs, oximetry, laboratory data (chemistries, hematology and urinalysis), ECGs, pulmonary function (spirometry), and physical examinations. AEs and SAEs including laboratory tests (chemistries, hematology, and urinalysis) and ECGs will be graded according to the National Cancer Institute (NCI) Common Terminology Criteria for Adverse Events Modified for CF (CTCAE v4.03).

8.1 Adverse Events

Information regarding occurrence of AEs will be captured throughout the study. Duration (start and stop dates), severity/grade, outcome, treatment and relationship to study drug will be recorded. Refer to Section 12.0, Assessment of Safety or Adverse Events and Serious Adverse Events.

8.2 Vital Signs

Blood pressure, heart rate, respiration rate, and temperature will be measured at rest in a sitting position. During the first 24 hours post first dose (SAD cohorts) or 12 hours post first dose (MAD cohorts), vital signs will be monitored via Holter and automated vital signs monitoring.

8.3 Telemetry

On dosing Day 1, continuous cardiac and vital signs monitoring will be conducted. Recorded measurements (eg, via Holter monitoring) are acceptable (if observed monitoring is not available).

8.4 Oximetry

Digital oximetry will be measured at rest in a sitting position.

8.5 Laboratory Evaluations

Laboratory evaluations will be performed according to the study schedule. For screening purposes, should the screening period require longer than 14 days (eg, CFTR genotype testing required longer than 14 days), safety evaluations (serum chemistries, hematologies, urinalysis, physical exam, vital signs, spirometry) must be re-obtained for confirmation of eligibility and enrollment into the study.

Serum chemistries will include sodium, potassium, chloride, bicarbonate, blood urea nitrogen (BUN), creatinine, glucose, calcium, phosphorus, SGPT/ALT, SGOT/AST, GGT, alkaline phosphatase, bilirubin (total and direct), uric acid, lactic dehydrogenase (LDH), albumin,

total protein, triglycerides, and cholesterol. Creatinine clearance is to be calculated using the Cockcroft-Gault equation adjusted for actual body weight. At screening, tocopherol (Vitamin E) levels will also be measured.

Hematologies will include a complete blood count: Complete blood count (CBC) with absolute differential (hematocrit, hemoglobin, white blood count, segmented neutrophils, bands, lymphocytes, monocytes, eosinophils, basophils, platelet count).

A Direct Antiglobulin Test (DAT) will also be performed at screening and 7 days after last dose.

Erythrocyte sedimentation rate (ESR) and C-reactive protein (CRP) will be measured at baseline, 24 hours post dose, and End of Study Visit for SAD cohorts, and at baseline, prior to doses 4, 7 and 10, and at the End of Treatment Visit for MAD cohorts. Two baseline measurements will be made; one on Day -1, and the other prior to dosing on Day 1.

Urinalysis (by visual inspection and dipstick) will include color and appearance, specific gravity, pH, protein, glucose, occult blood, ketones, bilirubin, leukocyte esterase, nitrite, and urobilinogen. In addition, microscopic analyses will be performed on samples with abnormal dipstick results. Urine microalbumin will be measured at baseline for SAD and MAD cohorts; end of study for SAD cohorts; and prior to dose 10 and end of study for MAD cohorts. Time of void will be recorded for each urine sample collected. At screening, testing for drugs of abuse will also be performed, specifically for amphetamines, methamphetamines, methylenedioxyamphetamine, cocaine, cannabinoids, phencyclidine, opiates, methadone, barbiturates, benzodiazepines, ethyl alcohol. Urine or blood testing for drugs of abuse is permitted.

Coagulation testing (INR, PT, PTT, fibrinogen) and total complement (CH50) will be performed at screening and the End of Study Visit for the SAD cohorts, and at screening, prior to dose 4, and at End of Treatment Visit for the MAD cohorts. Any abnormalities of coagulation will be followed with additional testing as determined by the Investigator and/or Medical Monitor to diagnose the coagulopathy.

For female subjects, a pregnancy test (preferably serum, but urine tests are also accepted) will also be obtained as designated by the study schedule.

Sputum for microbiology will be obtained as designated by the study schedule (for organism identification only).

8.6 Pharmacokinetic Evaluations

Samples for PK analysis will be collected as detailed in Appendix 1 and Appendix 2.

Expectorated sputum samples for PK assessment can be difficult to obtain at the specified time points. It is suggested that samples be collected in conjunction with spirometry, as often spirometry maneuvers can provoke coughing and sputum expectoration. Subjects should rinse their mouths with water or saline prior to collection of expectorated sputum samples.

Serum PK samples, when scheduled at time points when safety labs and/or biomarker samples are also to be collected, are to be collected first, followed by safety lab samples, and lastly biomarker samples.

Urine PK samples will be obtained over the following time intervals (in hours post dose administration completion): Pooled samples collected from 0 to 4 hours, 4 to 12 hours, and 12 to 24 hours post dose (SAD cohorts only), and at additional time points on subsequent study days (see Appendices 1 and 2 for specific timing of sample collection). Subjects should empty their bladders just prior to dosing and at the end of each time interval for the final urine collection of that interval. Urinalysis will be performed on each pooled sample prior to storage for PK analysis. Time and volume will be recorded for each void or urine collection interval at the designated time points.

8.7 Chest Xray

A chest radiograph should be obtained at screening for the SAD cohorts, and at end of study for subjects exhibiting pulmonary AEs. A chest radiograph or CT scan obtained within 90 days of Screening Visit is acceptable if there was no occurrence of intercurrent pulmonary illness during the interim.

A chest radiograph should be obtained at both screening and 7 days after last dose (end of treatment) for the MAD cohorts. A centralized reading of all chest radiographs may be performed at the end of the study.

8.8 Biomarkers

Immune response monitoring will be performed per Appendices 1 and 2. Biomarkers of interest will be measured in both blood and sputum, and may include cytokines and proteases. The immune profile seen may prompt further exploratory immune response biomarker analysis. Blood (serum and plasma) and expectorated sputum samples will be collected per the study schedule, and stored for later quantification.

8.9 Electrocardiogram (ECG)

12-lead ECG will be obtained at screening and end of study for the SAD cohorts, and at screening and 7 days post last dose for the MAD cohorts. 12-lead continuous telemetry will be obtained pre- and during the first 24 hours post first dose for SAD cohorts, and during the first 12 hours post first dose for MAD cohorts.

8.10 Pulmonary Function

Spirometry will be performed per American Thoracic Society (ATS)/European Respiratory Society (ERS) Standards. FEV₁, FVC, and FEF₂₅₋₇₅ will be collected. Actual liter values will be recorded. Prior to study drug dosing on a given day, the following order of concurrent treatment should be adhered to: Long- and/or Short acting bronchodilator, mucolytic therapy (eg,

Pulmozyme), chest physiotherapy (airway clearance technique), inhaled corticosteroid, inhaled antibiotics. Ancillary therapy regimens and airway clearance techniques should remain consistent throughout the study period, and the order of therapies and medications should also remain the same.

8.11 Physical Examination

Complete physical examinations (urogenital exams not required) will be performed at screening, Day -1, prior to dosing for dose Days 4, 7, 10, and 12 (Cohorts 5-8), and at the End of Treatment and End of Study Visits. Symptom-directed physical exams will be performed at all other time points, as indicated by the study schedule.

8.12 Height and Weight

Height will be measured using a calibrated, wall-mounted stadiometer and will be documented at the Screening Visit. Body weight will be measured using a calibrated scale per study schedule.

8.13 Sweat Chloride

Documentation of pilocarpine iontophoresis sweat chloride of > 60 mmol/L is required for eligibility for all subjects. As sweat chloride is a measure of exploratory efficacy in the MAD cohorts, sweat chloride will be measured by pilocarpine iontophoresis at screening for all subjects, at the dose 12 Visit, and at the End of Treatment and End of Study follow-up visits for the MAD cohorts only. Determination of sweat chloride must be performed in an accredited laboratory using a method accepted by the Cystic Fibrosis Foundation and documented accordingly.

The sweat chloride sample collection at the dose 12 Visit can be performed pre- or post-dose.

8.14 CFQ-R

The CFQ-R subject health-related quality of life questionnaire will be administered using the self-administered format (Adult version) [Appendix 3], according to the study schedule for MAD cohorts only. The CFQ-R will be administered prior to any other test or procedure on each of the required study days.

8.15 CFTR Genotyping and Sequencing

Confirmation of CFTR gene mutations homozygous for the $\Delta F508$ mutation are required for all subjects for eligibility. Genetic testing performed prior to the year 2000 must be re-confirmed, and a blood sample for CFTR genotyping should be obtained at the Screening Visit. Genotyping results must be received and confirmed as homozygous for the $\Delta F508$ mutation prior to randomization.

Complete CFTR gene sequencing will be performed for all subjects randomized into the study. Blood samples will be collected at baseline (Day -1 or Day 1 pre-dose), and stored until the end of the study for analysis.

Both CFTR genotyping and gene sequencing analysis are not optional for this study. Separate informed consent may be need to be obtained per local requirements.

9.0 OTHER CONSIDERATIONS

9.1 Routine CF Pulmonary Medications

Administer any routine pulmonary medications, including SABA and/or LABA, Pulmozyme, and inhaled corticosteroids and/or antibiotics, in the same order each dosing day, prior to spirometry and study drug dosing, during the in-house phase of the study.

9.2 Chest Physiotherapy

Any chest physiotherapy techniques utilized by an individual subject should remain consistent throughout the study. The order in which chest physiotherapy techniques are performed, in relation to other medications and administration of study drug should remain consistent throughout the study.

10.0 PHARMACOKINETIC AND EXPLORATORY EFFICACY MEASUREMENTS

10.1 Pharmacokinetic Measurements

Blood samples will be obtained from all subjects to obtain PK data pre- and post-dosing.

Samples for assessment of PK parameters of QR-010 (C_{max} , C_{min} , CL, V_d , AUC_{0-t} and $AUC_{0-\infty}$, and $t_{1/2}$) will be obtained only at the visits shown in Appendices 1 and 2.

10.2 Exploratory Efficacy Measurements

Exploratory efficacy response criteria will be evaluated per the schedule.

Efficacy Assessment 1

FEV₁

Efficacy Assessment 2

Sweat chloride measurement (MAD cohorts only)

Efficacy Assessment 3

CFQ-R Respiratory Symptoms Scale Score

Efficacy Assessment 4

Body weight

11.0 STUDY TERMINATION

If the Sponsor, DSMC, Sponsor's Medical Monitor or designee, study monitor, or appropriate regulatory officials discover conditions arising during the study that indicate that the study should be halted or that a study center should be terminated, this action may be taken after appropriate consultation. Termination may occur in accordance with the clauses contained in the site's executed clinical trial agreement. ProQR Therapeutics reserves the right to discontinue the trial prior to enrollment of the intended number of subjects, but intends only to exercise this right for valid scientific or administrative reasons.

If the clinical development of QR-010 is discontinued, the Sponsor shall immediately inform all trial Investigators/institutions and regulatory authorities. Study termination and follow-up will be performed in compliance with the conditions set forth in the ICH E6 on Good Clinical Practice guidelines and local regulatory requirements.

12.0 ASSESSMENT OF SAFETY OR ADVERSE EVENTS AND SERIOUS ADVERSE EVENTS

All subjects who receive study drug will be assessed for safety.

Investigators are responsible for monitoring the safety of subjects who have entered this study and for alerting the Sponsor regarding any event that seems unusual, even if this event may be considered an unanticipated benefit to the subject. The Investigator is responsible for appropriate medical care of subjects during the study.

12.1 Data Safety Monitoring Committee

An independent DSMC from the Cystic Fibrosis Foundation Therapeutics Development Network Data and Safety Monitoring Board will provide safety oversight for the study. All DSMC members have significant experience with oversight of cystic fibrosis clinical trials. A DSMC operational charter will be finalized prior to randomization of the first subject. The DSMC will review unblinded safety data from each cohort, and provide their recommendation for proceeding to the next dosing cohort, as described in Section 4.2.

12.2 Definitions of Adverse Event

12.2.1 Adverse Event

An AE is any untoward medical occurrence associated with the use of a drug in humans, whether or not considered drug related. AEs can include any unfavorable, noxious, unintended sign, symptom, or disease temporally associated with use of an investigational medicinal product or other protocol-imposed intervention, regardless of attribution. AEs may be spontaneously

reported by the subject, discovered by Investigator questioning, or detected through physical examination, laboratory test, or other means.

AEs include:

- Pre-existing medical conditions judged by the Investigator to have worsened in severity or frequency or changed in character during the protocol-specified AE reporting period
- AEs not previously observed in the subject that emerge during the protocol-specified AE reporting period (as specified in Section 12.4.1)
- Complications that occur as a result of protocol-mandated interventions (eg, invasive procedures such as blood draws)
- AEs that occur prior to assignment of study treatment that are related to a protocol-mandated intervention (eg, invasive procedures such as blood draws, medication washout, or no treatment run-in)

12.3 Assessment of Adverse Events

The Investigator is responsible for assessing the severity and causality of AEs.

12.3.1 Assessment of the Severity (Intensity) of Adverse Events

Maximum intensity is to be graded using the NCI CTCAE (V 4.0) Modified for CF (National Cancer Institute, 2011). If grading table does not have grading criteria for the event, the criteria in Table 4 will be used.

Table 4: Adverse Event Intensity (Severity) Scale

| Grade | Severity | Alternative Description of the Adverse Event ^a |
|-------|------------------|--------------------------------------------------------------------------------------------------------------------------------------------------------------------------------------------------------------------------------------------------------------------------------------------------|
| 1 | Mild | Asymptomatic or mild symptoms; clinical or diagnostic observations only; intervention not indicated. |
| 2 | Moderate | Minimal, local, or noninvasive intervention indicated; discomfort sufficient to reduce or interfere with daily activities. |
| 3 | Severe | Medically significant but not immediately life-threatening; hospitalization or prolongation of hospitalization may be indicated; disabling; limits self-care with significant interference with daily activities; incapacitating with inability to perform self care activities of daily living. |
| 4 | Life-threatening | Urgent intervention indicated; immediate risk of death. |
| 5 | Death | |

Note: Regardless of severity, some events may also meet regulatory serious criteria. Refer to definitions of an SAE.

- a. Use these alternative definitions for Grade 1, 2, 3, and 4 events when the observed or reported AE is not in the NCI CTCAE Modified for CF listing.

Any AE that meets the seriousness criteria (see Section 12.5, Serious Adverse Event Definition) will be considered an SAE, including all life-threatening AEs. In addition, AEs with Grade 4 intensity may be considered serious if the event is determined to be clinically significant.

12.3.2 Assessment of the Relationship of Adverse Events to Study Drug

The Investigator will make a causality assessment about the relationship of each AE to study drug. Treatment-related conditions must be distinguished from disease-related conditions. To ensure consistency of AE and SAE causality assessments, Investigators should apply the following general guideline:

Not Related: The AE has an etiology other than the study drug (eg, preexisting medical condition, underlying disease, intercurrent illness, or concomitant medication); and/or the AE has no plausible temporal relationship to administration of the study drug (eg, cancer diagnosed 2 days after first dose of study drug).

Related: There is a plausible (possible, probable, or definite) temporal relationship between the onset of the AE and administration of the investigational product, and the AE cannot be readily explained by the subject's clinical state, intercurrent illness, or concomitant therapies; and/or the AE follows a known pattern of response to the investigational product; and/or the AE abates or resolves upon discontinuation of the investigational product or dose reduction and, if applicable, reappears upon rechallenge.

Note: The Investigator's assessment of causality for individual AE reports is part of the study documentation process and will be recorded in the subject's medical record, AE CRF, and SAE form if applicable. AEs recorded without the Investigator's assessment of the relationship to study drug will be followed up until causality is assigned.

12.3.3 Assessment of the Outcome of Adverse Events

Recovered/resolved: The subject has fully recovered from the event, with no residual effects observable.

Recovered/resolved with sequelae: The subject has recovered from the event, but with residual sequelae effects observable.

Not recovered/resolved: Effects of the event are still present.

Recovering/resolving: The subject has improved, but has not fully recovered from the event.

Fatal: The death is related to the event.

Unknown: The outcome of the event is unknown to the reporter (eg, subject was lost to follow-up).

12.4 Reporting of Adverse Events

The Investigator is responsible for ensuring that all AEs and SAEs are recorded in the source document, AE CRF, and/or SAE form, and reported to the Sponsor in accordance with protocol instructions.

12.4.1 Adverse Event Reporting Period

All significant medical conditions including signs/symptoms of the underlying diagnosis found during the screening period and up to randomization will be captured as medical history. Any event/condition related to participation in the trial but not related to underlying or concomitant disease that is noted after screening up to the randomization date will be captured as a non-treatment emergent AE.

Any event/condition noted once the subject is randomized will be captured as an AE. All AEs and SAEs regardless of attribution will be collected until at least 30 days following the last administration of study treatment or initiation of new therapy, whichever is earlier. At the last scheduled visit, the Investigator should instruct each subject to report to the Investigator any subsequent SAEs that the subject's personal physician believes could be related to prior study treatment. Any related non-serious AE occurring after the reporting period may be reported at the discretion of the Investigator.

AEs and SAEs related to study drug that persist >30 days after the last study drug dose should be followed until resolution or until they return to baseline, stabilize, the subject is lost to follow-up, or it has been determined that the study treatment or participation is not the cause of the AE/SAE. Resolution of AEs and SAEs (with dates) should be documented on the AE CRF and SAE form (if applicable) and in the subject's medical record to facilitate source data verification. For some SAEs, the Sponsor or its designee may follow up by telephone, facsimile, electronic mail, and/or a monitoring visit to obtain additional case details deemed necessary to appropriately evaluate the SAE report (eg, hospital discharge summary, consultant report, or autopsy report).

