1.0 SYNOPSIS

| | | |
|-----------------------------------------------------------------------------|---------------------------------------------------------------------------------------------------------------------------------------------------------------------------------------------------------------------------------------------------------------------------------------------------------------------------------------------------------------------------------------------------------------------------------------------------------------------------------------------------------------------------------------------------------------------------------------------------------------------------------------------------------------------------------------------------------------------------------------------------------------------------------------------------------------------------------------------------------------------------------------------------------------------------------------------------------------------------------------------------------------------------------------------------------------------------------------------------------------------------------------------------------------------------------|------------------------------------------|
| Name of Sponsor/Company: ProQR Therapeutics | Individual Study Table Referring to Part of the Dossier Volume: NA | (For National Authority Use only) |
| Name of Investigational Product: QR-010 Solution for Nebulization | Page: NA | |
| Name of Active Ingredient: QR-010 | | |
| Title of Study: | Phase 1b, Randomized, Double-blind, Placebo-controlled, Dose Escalation Study to Evaluate the Safety, Tolerability and Pharmacokinetics of QR-010 in Subjects With Homozygous $\Delta F508$ Cystic Fibrosis | |
| Investigators: | To be determined | |
| Study Centers: | Approximately 27 centers in North America and European Union (EU) | |
| Phase of Development: | 1b | |
| Study Period: | 24 months | |
| Duration of Subject Participation: | 9 days (single ascending dose cohorts) 8 weeks (multiple ascending dose cohorts) | |

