4.0 STUDY OVERVIEW

4.1 Criteria for Evaluation

4.1.1 Primary Endpoint

- Incidence and severity of adverse events (AEs) from baseline through end of study
- Occurrence of dose-limiting toxicities (DLT) in each dose cohort from baseline through end of study

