4.2 Study Design

The study is a multicenter, randomized, double-blind, and placebo-controlled Phase 1b SAD and MAD design. The subject, investigator, and site personnel (except pharmacist) will be blinded to treatment, while the sponsor will be unblinded. Sponsor personnel will be unblinded to subject

treatments in order to permit real-time interpretation of the safety, pharmacokinetic, and pharmacodynamic data. The site monitor will remain blinded to individual subject treatment allocation until all monitoring of study data has been completed. To minimize the potential for bias, individual subject treatment randomization information will not be released to the investigator or blinded study site personnel until the study database has been locked.

Eligible subjects with homozygous $\Delta F508$ CF will be randomized at a 3:1 ratio to receive either QR-010 or placebo via oral inhalation (nebulization). This study will be conducted in North America and select European countries.

[figure not shown]
The study includes 2 stages. The first stage is a single ascending dose-escalation (SAD) design to determine safety and tolerability of a single dose of QR-010. The second stage is a multiple ascending dose escalation (MAD) design to further assess the safety, tolerability, and exploratory efficacy of 12 doses of QR-010 over 4 weeks. All doses will be administered in a clinical setting.

For the SAD cohorts, subjects will receive the dose in an inpatient observation unit and be observed for a total 4 days, and will be discharged on Day 4. Subjects will return for PK and safety follow-up as an outpatient on Day 8 (End of Study Visit).

For the MAD cohorts, subjects will receive doses 1 through 12 in a clinic while under observation. On Day 1 and Day 3 subjects will be observed until 12 hours post dose. Following the last dose (dose 12), subjects will return twice for PK sampling, and will be evaluated 7 and 28 days after the last visit for this additional safety monitoring and sampling for PK.

A schematic of the study design is presented in Figure 3.

Figure 3: PQ-010-001 Study Schematic

Single Ascending Dose Escalation Cohorts: The first two subjects of each cohort may be dosed on the same day, at least 4 hours apart. If no significant AEs occur, the remainder of the cohort may be dosed at least 24 hours later, with at least 1 hour between subjects.

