7.1 Visit and Assessment Windows

The flexibility regarding scheduling of study days and corresponding procedures differ depending on the cohort and phase of the study. The timing of assessments, procedures and sample collections outlined in the protocol are nominal times. It is understood that in the phase 1 setting, actual times will approximate rather than match the nominal times exactly. Actual times are to be recorded in the source documentation and in the case report forms (CRFs), and, if any time points are missed, the reasons are also recorded.

For the SAD cohorts, there is no flexibility regarding the timing of the scheduled study days in relation to dose Day 1.

For the MAD cohorts, there is some flexibility regarding the timing of the scheduled study days in relation to dose Day 1. The description of procedures assumes a Monday-Wednesday-Friday dosing schedule. An alternative dosing schedule can be used, provided that there is at a minimum 2 days between doses, and a maximum of 4 days between doses. Missed doses are to be recorded as such, and the overall treatment period should remain at 4 weeks, and not be extended to accommodate the missed doses. Missed doses are to be recorded in the CRF.

Details regarding acceptable windows for timing of study procedures for both the SAD and MAD cohorts can be found in the Laboratory Manual.

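### Section 12.4.1 promises at least 30 days of all-cause AE collection, but no scheduled contact supports it after Day 8 in SAD, and the SAP sets no end date for TEAEs

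*Protocol*

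**What the plan says.** Protocol Section 12.4.1 sets the reporting period. Events of any cause, serious or not, are covered, and the text is that they "will be collected until at least 30 days following the last administration of study treatment or initiation of new therapy, whichever is earlier". The same section then describes what happens after the visits end: "At the last scheduled visit, the Investigator should instruct each subject to report to the Investigator any subsequent SAEs", limited to those that the subject's own physician thinks could be related to treatment.

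The schedule is set elsewhere:

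- **SAD, Section 4.2:** "Subjects will return for PK and safety follow-up as an outpatient on Day 8 (End of Study Visit". Section 7.1 adds: "For the SAD cohorts, there is no flexibility regarding the timing of the scheduled study days in relation to dose Day 1".
- **MAD, Section 7.4.12:** "Follow-up visits will occur 7 and 28 days after the last dose of study drug (dose 12". Subjects who stop early "should also return to the clinic to complete the End of Study Visit procedures 28 days after the last study drug dose".
- **Synopsis, duration of participation:** "9 days (single ascending dose cohorts) 8 weeks (multiple ascending dose cohorts".

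The primary endpoint in Section 4.1.1 has its own window: "Incidence and severity of adverse events (AEs) from baseline through end of study". SAP Section 4.10.1.1 counts an event as treatment-emergent if it starts at or after the first dose, and gives no closing date. The protocol's definition in Section 13.7.1 gives none either.

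**The concern.** Three windows apply to one set of data: 30 days in Section 12.4.1, end of study in Section 4.1.1, and no limit in the SAP. Section 12.4.2 has AEs elicited by questioning at evaluation time points, and Appendix 1 places AE review only at visits. Once visits stop, nothing planned asks a subject about new events that are non-serious or not thought related.

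This is a first-in-human study with six QR-010 subjects per cohort, so single events show in the tables. A SAD event on Day 20 enters the treatment-emergent table if the subject happens to mention it. The same event is absent if the subject does not. A reader of the report who takes Section 12.4.1 at face value would believe that SAD subjects were observed for 30 days. Sites would also be unsure whether SAD Days 9 to 31 are in scope for active collection.

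**Working it through.** **Inputs.** SAD dose on Day 1 and last visit on Day 8 (protocol Appendix 1, Table A.1-1). MAD dose 12 on Day 26 (Table A.1-5), with follow-up visits on Days 33 and 54 (Table A.1-6). Stated window of 30 days after the last dose (Section 12.4.1). Six QR-010 subjects per cohort (Section 13.2).

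**Step 1: the schedule's own numbering.**

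- SAD: 8 − 1 = 7 days after the dose; 7 × 24 = 168 h, as Table A.1-1 shows.
- MAD End of Treatment: 33 − 26 = 7 days after dose 12; (33 − 1) × 24 = 768 h after dose 1, as Table A.1-6 shows.
- MAD End of Study: 54 − 26 = 28 days after dose 12; (54 − 1) × 24 = 1272 h after dose 1, as Table A.1-6 shows.

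The numbering is consistent, so the gap does not come from a miscounted day.

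**Step 2: stated window against last scheduled contact.** Gap = (day of last dose + 30) − day of last visit.

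| Part | Window reaches | Last visit | Gap | Share of 30 days |
|---|---|---|---|---|
| SAD | 1 + 30 = Day 31 | Day 8 | 23 days | 23/30 = 77% |
| MAD | 26 + 30 = Day 56 | Day 54 | 2 days | 2/30 = 7% |

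These are maxima for a subject who attends the scheduled visits, because Section 12.4.1 closes the window when new therapy starts, if that comes sooner. For a SAD subject who starts new therapy by Day 8, the gap is 0. The range is therefore 0 to 23 days in SAD and 0 to 2 days in MAD. The documents do not say how many subjects would start new therapy.

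**Step 3: do other provisions fill the gap?**

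- Section 12.4.1, instruction at the last visit: subject-initiated, and only SAEs that a physician thinks could be related.
- Section 12.7: a duty to report SAEs after participation, but only those the investigator considers possibly related.
- Section 12.4.1, follow-up beyond 30 days: only related events that persist, not new ones.
- Section 5.5.1, SAD subjects re-entering in MAD: only after at least 90 days, which is past the window.

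None of these actively collects new events regardless of attribution.

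**Step 4: effect on a table.** One volunteered late event in a cohort with none otherwise moves QR-010 incidence from 0/6 = 0% to 1/6 = 17%. If it goes unmentioned, the table stays at 0%.

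**The case against.** The strongest reply is that nothing important depends on the 30 days, and much of it stands.

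- **Primary endpoint.** A reader might infer that the primary endpoint is under-ascertained. The documents do not support that. Section 4.1.1 ends it at end of study, which is Day 8 in SAD and 28 days after the last dose in MAD, and the visits cover both.
- **Dose escalation.** A reader might also fear for the escalation decisions. Sections 4.2 and 4.3 base them on 7 days of follow-up after dosing, which the schedule delivers.
- **Feasibility.** It would be too strong to say that the window cannot be delivered, or that all contact ends. Section 12.4 makes the investigator responsible for recording all AEs, no text forbids an unscheduled call, and some reporting continues. What is missing is a scheduled contact.
- **Bias between arms.** Subjects, investigators and site staff other than the pharmacist are blinded, and both arms of a cohort share one schedule. No mechanism for differential ascertainment between QR-010 and placebo is apparent. The problem is an undefined observation period and added noise.
- **The open-ended TEAE definition.** It loses no recorded event. That is true, but it leaves the denominator of observation time unstated.

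A further caution concerns the remedy. Section 12.4.3(e) ties the recording of all deaths to the period in Section 12.4.1. Simply ending that period at Day 8 would also cut the SAD death-reporting window from 30 days to 7.

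**Conclusion.** The inconsistency is real and is essentially a SAD matter: up to 23 of the 30 stated days have no planned ascertainment of new AEs regardless of attribution. The MAD shortfall of up to 2 days is trivial and needs only tidying.

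The conclusion assumes that the sections and appendices supplied show every scheduled contact, that subjects complete the visits, and that no new therapy closes the window early. The consequence is limited to what the safety tables mean. SAD summaries would combine systematic questioning to Day 8 with unsystematic reports afterwards, in cohorts where one event is worth 17 percentage points. The documents do not settle which follow-up length is right, so the finding is that the passages must be reconciled, not that either period is wrong. It should be corrected, but it does not threaten the primary endpoint or the escalation scheme.

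**What to change.** 1. **Reconcile the protocol.** Bring Section 12.4.1 into line with Sections 4.1.1, 4.2, 7.3.6 and 7.4.12 in one of two ways; the choice is the sponsor's.
   - Keep the stated window and schedule one telephone AE/SAE query at its end: on or after Day 31 in SAD and Day 56 in MAD under the present text. Cost: one call per subject, plus a line in the schedule of assessments. If SAD follow-up is already over, this option is closed for those subjects.
   - Restate the all-AE collection period as ending at the End of Study Visit, and give SAEs after that visit, and the death reporting in Section 12.4.3(e), an explicit period of their own so that neither is shortened by accident. Cost: wording only, with a shorter stated window for non-serious events.
2. **Align the SAP.** In Section 4.10.1.1, limit the TEAE summaries to events starting from the first dose up to the chosen cut-off, the same for every subject within each study part. List later events separately. Say how the new-therapy clause is handled, since it would otherwise give subjects different end points. Cost: one sentence and one additional listing.
3. **State the observation window** in the titles or footnotes of the SAD and MAD AE tables, so that a reader can see what period the incidences describe.
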